5.4 Method for Assigning Subjects to Treatment Groups

Not applicable.

5.5 Preparation and Administration of Study Imaging Agent

The Cu-64 peptide analog will be prepared using the methods described previously. Sterile reagents and glassware will be used. The dose, no more than five mL in volume, will be dispensed. Sterility tests will be performed and recorded. To maintain the procedure uniformity, we will prepare kits and use them for instant Cu-64 labeling. HPLC analysis will also be performed for determination of radiochemical purity and data recorded.

Four ±10% mCi of Cu-64-TP3805, prepared as described here in will be injected through an indwelling intravenous line and the lines will be flushed with 5 ml sterile 0.9% saline.

5.6 Subject Compliance Monitoring

Not applicable.

5.7 Prior and Concomitant Therapy

Not applicable.

6.0 STUDY PROCEDURES

6.1 Study Visit Schedule (see appendix 15.1)

Screening

Potential subjects identified by the urologic oncologists (Drs. [name], [name] and [name]) who have persistently elevated PSA, 4 or greater and scheduled for MRI fusion/TRUS. The clinical coordinator will screen the patient for eligibility as per the inclusion and exclusion criteria. Eligible subjects will review and sign the informed consent. The coordinator will schedule the Cu-64-TP3805 PET imaging study at least one week but not more than 3 weeks before their scheduled MRI Fusion/TURS biopsy

Visit 1

The clinical coordinator will meet the subject and guide them through the imaging process. They will monitor the patient before, during and after the imaging study, as previously described.

Follow-up

The clinical coordinator will follow up with the subjects by phone the day after the study imaging procedure to ensure that there were no adverse reactions. The coordinators will be available as needed for the time period until their scheduled biopsy procedure for questions or concerns.

7.0 STATISTICAL PLAN

7.1 Sample Size Determination

7.2 We will study 20 patients with persistently elevated PSA for a Cu-64 PET imaging in whom biopsy are ordered. These patients shall be PET imaged with our Cu-64 peptide probe first and then a week or so later the image guided biopsy shall be performed. The image guided biopsy is the standard of care procedure. The objective is to validate the PET imaging results with the histology of biopsy results. Generally, approximately 60% of the patients with elevated PSA have prostate cancer. We expect 80% accuracy in identifying 20 subjects as having histologically determined cancer/absence of cancer. The 95% confidence interval of this level of accuracy for this sample size is + or – 17.5%. Thus we expect to find an accuracy level between 62.5% to 97.5%. Please note this is a pilot study, not designed to be an efficacy determination trial. **Statistical Methods**

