1.2 Background and Rationale

Cancer is complex yet commonplace, and the most terrifying disease of mankind. Among men in the USA, PC is particularly lethal, second only to cancers of the lung and bronchus combined [1]. In 2010, more than 30,000 men succumbed to PC and more than 240,000 new PC cases were identified in the USA [1]. PC affects one in every 6 men who are 60 years or older and affects African-Americans at a rate 2.4 times greater than European-Americans [1]. Great strides have been made both in diagnosis and treatment of PC. However, the PC-related death rate has not yet declined, and the quality of life of survivors has not yet improved [1]. Three prominent screening tests, the digital rectal examination, MRI, and a blood test for prostate specific antigen (PSA) determination play a significant role in detecting pathologically advanced PC. However, they are not considered reliable tools for early warning of PC [2], [3], [4] nor can they be used reliably to detect recurrent cancer or to determine

metastatic status of the disease. The lack of reliable diagnosis, results in undertreatment or overtreatment of patients with minimal benefit, enormous morbidity, incontinence, and/or impotence. Therefore, histology remains the mainstay of PC confirmation. However, out of >750,000 biopsies performed each year in the USA, >65% show benign pathology, and cost hundreds of millions of health care dollars. Various imaging techniques have been evaluated, but their utility to image suspected PC or its metastatic lesions is not fully dependable [3]. Furthermore, monitoring the effectiveness of PC therapy continues to be a challenge.

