The need for developing oncogene receptor specific agents, such as those proposed here, is compelling. The primary tools for PC screening, the serum PSA and the digital rectal examination are neither specific nor sensitive, as many men with elevated PSA have been found not to have PC [2]. Transrectal ultrasonography (TRUS) provides an axial and sagital examination of the prostate gland, and allows physicians to estimate its volume. However, in 60-70% of PC cases are hypoechoic and thus invisible by TRUS [3]. Histologic examination, therefore, remains the gold standard for PC but requires an invasive procedure for tissue sampling. By this time, the PC is usually advanced. However, the question still remains as to where to direct the needle for biopsy. As a result, out of the approximately 750,000 prostate biopsies that will be performed in the USA in 2010, more than 2/3 will find benign pathology [17].

The use of contrast enhanced spiral computerized x-ray tomography (CT) is limited to advanced, high-grade tumors [18]. Using 3D MR spectroscopic imaging, PC was diagnosed as possible if the ratio of choline to citrate exceeded 2SD above the normal population and definite if the ratio exceeded 3SD above the normal population [19]. However, sensitivity and specificity were only 80% and 46%, respectively [20]. Dynamic contrast enhanced MRI (DCE-MRI) is known to be a powerful tool for localization of vascular solid tumors [21].

DCE-MRI however has low sensitivity (50%) [22] and has not been able to distinguish between PC and benign prostatic hyperplasia (BPH) [23]. T2 weighted endorectal MRI also has low accuracy of PC detection [24]. Much more work therefore, is needed to be done [25].

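### Section 7 plans only overall accuracy, which depends on case mix: 16 of 20 correct would not rule out a scan that calls every man the same, at the 60% cancer rate or at the background rates

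*Combined protocol and SAP*

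**What the plan says.** Section 7.1 sets the sample: "We will study 20 patients with persistently elevated PSA for a Cu-64 PET imaging in whom biopsy are ordered". The target is patient-level accuracy: "We expect 80% accuracy in identifying 20 subjects as having histologically determined cancer/absence of cancer". Its precision is stated as "The 95% confidence interval of this level of accuracy for this sample size is + or – 17.5" percent, that is 62.5% to 97.5%. The same paragraph gives the case mix, "Generally, approximately 60% of the patients with elevated PSA have prostate cancer", and describes the trial as a pilot that is not meant to determine efficacy. The Study Summary repeats all of this. In the text available, no source is given for the 60%. Sensitivity, specificity, a reference value for accuracy and an interval method are not mentioned either.

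Section 1.2 gives two figures on biopsy results. Its opening says "out of >750,000 biopsies performed each year in the USA, >65% show benign pathology". The later paragraph on screening tools says of roughly the same 750,000 biopsies that "more than 2/3 will find benign pathology".

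Section 6.1 describes the men enrolled: PSA persistently 4 or greater and scheduled for MRI fusion/TRUS biopsy.

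**The concern.** The statistical plan expects six cancers in ten men. The rationale for the trial rests on fewer than about one biopsy in three showing cancer. Nothing in the protocol explains why this cohort should yield nearly twice as much.

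The gap matters because overall accuracy mixes two quantities, sensitivity and specificity, weighted by the numbers of men with and without cancer. A scan with no diagnostic information can score well by always giving the commoner answer. If accuracy is the only statistic reported, a reader cannot tell whether 80% reflects detection of cancer, which is the primary objective in Section 2.1, or the composition of the sample.

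**Working it through.** **Inputs.** From Section 7.1: n = 20, expected accuracy 0.80, 95% two-sided interval, cancer proportion 0.60. From Section 1.2: benign share above 65% and above 2/3, so cancer share below 35% and below 33.3%.

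**1. The plan's own interval.** The Wald half-width is 1.96 × √(0.80 × 0.20 / 20) = 1.96 × 0.0894 = 0.175, giving 62.5% to 97.5%. This reproduces the stated figure. The cancer rate does not enter the formula.

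**2. Expected counts and the score of an uninformative scan.** With cancer proportion p, expected cancers are 20p. A scan that calls everyone the commoner class scores max(p, 1 − p).

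| Cancer proportion | Cancers / benign | Score from calling all the same |
|---|---|---|
| 60% | 12 / 8 | 60% |
| 35% | 7 / 13 | 65% |
| 33.3% | 6.7 / 13.3 | 66.7% |

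Because Section 1.2 says more than 65% and more than two thirds are benign, 7 cancers is the upper end under those figures.

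**3. Does the expected result exclude those scores?** Expected accuracy of 80% is 16/20. The exact (Clopper-Pearson) limits are the 2.5% point of Beta(16, 5) and the 97.5% point of Beta(17, 4), which give 56.3% and 94.3%. The interval contains 60%, 65% and 66.7%. The Wilson interval, 58.4% to 91.9%, also contains all three. Only the Wald lower limit of 62.5% falls between 60% and 65%.

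**4. What 16/20 can conceal.** With 12 cancers and 8 benign, 16 correct could be 12/12 and 4/8 (sensitivity 100%, specificity 50%) or 8/12 and 8/8 (67%, 100%). With 7 and 13, it could be 7/7 and 9/13 (100%, 69%) or 3/7 and 13/13 (43%, 100%). The same 80% accuracy is compatible with sensitivity from 43% to 100%.

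**5. Precision of the two components.** Two splits that each give 16/20, with exact 95% intervals:

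| Case mix | Sensitivity | Specificity |
|---|---|---|
| 12 / 8 | 10/12: 51.6% to 97.9% | 6/8: 34.9% to 96.8% |
| 7 / 13 | 6/7: 42.1% to 99.6% | 10/13: 46.2% to 95.0% |

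The point estimates differ because the counts are whole numbers. At a common 80%, the Wald half-width 1.96 × √(0.16/m) is 22.6 points for m = 12, 29.6 for m = 7, 27.7 for m = 8 and 21.7 for m = 13. Fewer cancers widen the sensitivity interval and narrow the specificity interval.

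**The case against.** A reader might infer four stronger things, and the documents support none of them.

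- **That the 60% contradicts Section 1.2.** The 60% is about men with elevated PSA; the benign rates are about all US prostate biopsies. In the later paragraph, Section 1.2 presents the high benign rate as following from uncertainty about where to place the needle. The trial uses image-guided biopsy in selected men, so a higher yield is plausible and both figures could be true. Nor are the two benign figures clearly independent, since both refer to about 750,000 biopsies a year.
- **That a wrong 60% would upset the sample size or the interval.** Step 1 shows that it enters neither. The observed case mix will replace it at analysis.
- **That the choice of rate decides whether 80% beats an uninformative scan.** The 60% lies outside the stated range and 65% to 67% lies inside it, but this rests on the Wald limit. The exact interval covers all of these values.
- **That fewer cancers simply cost precision.** Sensitivity loses and specificity gains.

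It is also fair to say that the protocol sets no null value or success rule and disclaims an efficacy determination. Comparison with the commoner class is therefore a reading aid suggested here, not a test that the plan fails.

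What remains is unaffected by these points. The objective is still the ability to detect cancer, and the single planned statistic does not measure that by itself, whichever rate is right. A pilot label does not make accuracy interpretable without its components.

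**Conclusion.** The concern holds in a limited form. The 60% is unsourced and unreconciled with Section 1.2, which is a gap in justification and not a demonstrated error. The substantive weakness is that overall accuracy is the only planned statistic. An uninformative scan scores 60% at the planning rate and 65% to 67% at the background rates. The expected 16/20 excludes none of these on an exact interval, and it is compatible with very different sensitivities.

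This rests on patient-level classification in all 20 men, with 16 correct. It also has a limit. If 9 to 11 men proved to have cancer, the larger class would be 50% to 55%, below the exact lower limit of 56.3%. Accuracy would then clear that mark but would still not separate sensitivity from specificity. The documents give no biopsy yield for the trial's own population, so the 33% to 60% range is only what the protocol's figures span.

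**What to change.** In Section 7 and the Study Summary:

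1. Report sensitivity and specificity with exact (Clopper-Pearson) 95% intervals beside accuracy.
2. Give accuracy an exact interval. For 16/20 this replaces 62.5% to 97.5% with 56.3% to 94.3%.
3. State that accuracy will be interpreted against the larger of the observed cancer and non-cancer proportions, as description and not as a success rule.
4. Either justify 60% for men having MRI fusion/TRUS biopsy and say why it differs from Section 1.2, or show expected counts over about 33% to 60%: 7 to 12 cancers and 13 to 8 benign.

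The cost is wording. The component intervals are wide and the accuracy interval has a lower floor, so the stated expectations look less favourable. No more patients or procedures are needed.

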Study Duration	3 years
Study Center(s)	Single-center.
Objectives	The objective is to validate the PET imaging results of Cu-64-TP3805, with the histology of the image guided biopsy results. Generally, approximately 60% of the patients with elevated PSA have prostate cancer
Number of Subjects	20
Diagnosis and Main Inclusion Criteria	We will study 20 patients with persistently elevated PSA whom are scheduled for biopsy These patients shall be PET imaged with our Cu-64 peptide probe first and then a week or so later the image guided biopsy shall be performed. The image guided biopsy is the standard of care procedure. The objective is to validate the PET imaging results with the histology of biopsy results. Generally, approximately 60% of the patients with elevated PSA have prostate cancer. We expect 80% accuracy in identifying 20 subjects as having histologically determined cancer/absence of cancer. The 95% confidence interval of this level of accuracy for this sample size is + or – 17.5%. Thus we expect to find an accuracy level between 62.5% to 97.5%. Please note this is a pilot study, not designed to be an efficacy determination trial.
Study Therapy, Dose, Route, Regimen	Cu-64-TP3805, a novel PET imaging molecule, given as a single intravenous injection dose of (4 mCi ±10%).
Duration of administration and follow-up	Single Intravenous administration given over 5 minutes and patients observed for 90 min; follow up, call 24 hrs later.
Reference therapy	N/A

Statistical Methodology	We expect 80% accuracy in identifying 20 subjects as having histologically determined cancer/absence of cancer. The 95% confidence interval of this level of accuracy for this sample size is + or – 17.5%. Thus we expect to find an accuracy level between 62.5% to 97.5%. Please note this is a pilot study, not designed to be an efficacy determination trial.
Schema	Subjects will undergo Cu-64-TP3805 PET Imaging at least one week prior to biopsy. Investigational PET imaging will be analyzed and compared to biopsy pathology to determine efficacy in detection and localization of PC foci. Urine sample will be collected prior to Cu-64 injection and 90 minutes post injection prior to imaging

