1.1 Specific Aims and Hypothesis

We hypothesize that targeting VPAC1 receptors overexpressed on PC cell surfaces with a Cu-64 imaging agent, TP3805 will provide a specific and sensitive means for molecular diagnosis of PC at an early stage, to determine its recurrence, and to image metastases.

Our specific aim is to assess the ability of Cu-64-TP3805 to detect PC within the prostate gland.

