Methods: 25 men scheduled for radical prostatectomy and who signed IRB approved consent form were PET imaged preoperatively. Standardized Uptake Values (SUVs) were determined, malignant lesions (SUV > 1.0) were counted, and data compared with histologic findings. In addition, de-paraffinized whole mount pathology slides (n=68) from 6 VPAC1 PET imaged patients, 3 benign prostatic hyperplasia (BPH) patients (n=9), one malignant lymph node (n=3), and one benign lymph node (n=3) were incubated with ⁶⁴Cu-TP3805, washed with PBS, dried and subjected to digital autoradiography (DAR). Slides were then H&E stained, read by a pathologist, and DAR images were compared with foci delineated as PC, benign, cyst, or prostatic intraepithelial neoplasia (PIN).

Results: In 25 patients, 212 lesions had SUVs > 1.0 as compared to 127 lesions identified by histology. While the status of the remaining 85 PET lesions remains to be determined, in 68 histological slides from 6 PET imaged patients, DAR identified 105/107 PC foci (missed 2 due to artifact), 19/19 high grade PIN (HGPIN), 2/2 ejaculatory ducts (ED) and 5/5 urethra verumontanum (UV). Additionally, DAR found 9 PC lesions not previously identified by histology. The positive and the benign lymph nodes were correctly identified by DAR, and for the 3/3 BPH patients without PC, and 5/5 cysts, DAR was negative.

Conclusion: ⁶⁴Cu-TP3805, a VPAC1 receptor specific biomolecule delineates PC lesions in vivo and ex vivo, provides normal images for benign masses, and is worthy of further studies in patients.

In this investigation, we will use the same preparation, Cu-64-TP3805 that has been prepared and used in the previous human subjects with 100% success. Although no preparation will either be compounded or used out of the Jefferson campus, we will use a "kit" that will be ready to be heated following the

addition of 440 μ L of sterile H2O and then Cu-64 activity. These kits will contain all chemicals in sterile, 10 mL glass vials. Reagents will be added to the vial, snap frozen in dry ice, lyophilized and the vials will be sealed in N2 atmosphere. They will be stored at 4°C and examined for Cu-64 labeling and shelf life stability.

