2.0 STUDY OBJECTIVES

2.1 Primary Objective:

The primary objective of this study is to assess the ability of Cu-64-TP3805 to detect Prostate cancer in patients with persistently elevated PSA.

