3.2 Primary Study Endpoints

The primary endpoint of study will be to determine the ability of Cu-64-TP3805 to detect PC foci within the prostate gland in patients with persistialy elevated PSA as compared with tumor maps derived by histology of biopsy specimens obtained guided biopsy.

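### The primary endpoint is detection of cancer foci against biopsy tumor maps, but the only planned statistic is per-patient accuracy, so the endpoint has no estimate and neither sensitivity nor specificity is planned

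*Combined protocol and SAP*

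**What the plan says.** The documents describe the target of the study at two levels.

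- **Patient level.** Section 2.1 gives the primary objective as the ability "to detect Prostate cancer in patients with persistently elevated PSA". Section 7.1 says "We expect 80% accuracy in identifying 20 subjects as having histologically determined cancer/absence of cancer", with a 95% interval of ±17.5 points (62.5% to 97.5%) and about 60% of men expected to have cancer. The Statistical Methodology row of the Study Summary repeats this.
- **Focus level.** The primary endpoint in section 3.2 is the ability to "detect PC foci within the prostate gland in patients with persistialy elevated PSA as compared with tumor maps derived by histology of biopsy specimens". The Schema in the Study Summary says PET will be "compared to biopsy pathology to determine efficacy in detection and localization of PC foci". The PET form in section 15.2 records visible foci by sextant, with SUV and size.

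The hypothesis in section 1.1 is that the agent "will provide a specific and sensitive means for molecular diagnosis of PC". Sensitivity and specificity otherwise appear only in the background and in earlier results, never as quantities this study will estimate. No section says how PET foci are to be matched to biopsy findings, or how such a comparison would be summarised.

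**The concern.** There are two gaps.

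**(a) Endpoint and statistic use different units.** A single cancer/no-cancer call per man cannot be set against a tumor map. A man whose PET focus lies in one sextant and whose cancer lies in another counts as correct. Followed as written, the plan leaves its named primary endpoint without an estimate, and its stated precision does not apply to foci. With 2.1 and 3.2 pointing to different units, the unit of analysis could also be chosen after the results are known.

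**(b) Accuracy is the only summary.** It mixes performance in men with cancer and men without, weighted by how many of each are enrolled. An 80% result would not say whether the agent finds cancer, excludes it, or does both, and it would not carry over to a population with a different cancer rate. The next study would need exactly that information.

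**Working it through.** **1. The plan's own figure.** Inputs from section 7.1: expected accuracy 0.80, n = 20, 95% level. Wald half-width = 1.96 × √(0.80 × 0.20 / 20) = 0.175, giving 62.5% to 97.5%. This agrees with the plan. The arithmetic is sound; the question is what is being estimated.

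**2. What 80% accuracy can mean.** At 60% cancer, 0.60 × 20 = 12 men have cancer and 8 do not. Accuracy of 80% is 16 correct. The possible splits run from 8 + 8 to 12 + 4. The two ends and the middle, with exact (Clopper-Pearson) 95% intervals:

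| Correct with / without cancer | Sensitivity | Specificity |
|---|---|---|
| 8 + 8 | 8/12 = 67% (34.9% to 90.1%) | 8/8 = 100% (63.1% to 100%) |
| 10 + 6 | 10/12 = 83% (51.6% to 97.9%) | 6/8 = 75% (34.9% to 96.8%) |
| 12 + 4 | 12/12 = 100% (73.5% to 100%) | 4/8 = 50% (15.7% to 84.3%) |

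All three would be reported as 80%.

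**3. Dependence on the cancer rate.** Accuracy = rate × sensitivity + (1 − rate) × specificity. The 60% is uncertain: section 1.2 cites biopsy series in which more than 65%, or more than two thirds, were benign. Take the two end rows of the table at a cancer rate of one third:

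- Sensitivity 100%, specificity 50%: 1/3 × 1 + 2/3 × 0.5 = 67%.
- Sensitivity 67%, specificity 100%: 1/3 × 2/3 + 2/3 × 1 = 89%.

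Two tests that both score 80% at a 60% cancer rate score 67% and 89% at one third.

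**4. A no-information reference.** On the 12/8 split, calling every man positive scores 12/20 = 60%. This lies inside the exact interval for 16/20 (56.3% to 94.3%) and the Wilson interval (58.4% to 91.9%), but just outside the plan's Wald interval (62.5% to 97.5%).

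**5. Focus level.** No interval can be calculated for the 3.2 endpoint. The documents give no expected number of foci per man for biopsy, no detection rate per focus and no within-patient correlation. For scale only, section 1.8 reports on an earlier prostate series with this agent: "In 25 patients, 212 lesions had SUVs > 1.0 as compared to 127 lesions identified by histology". That is 212/25 = 8.5 PET lesions per man against 127/25 = 5.1 by histology. The status of 212 − 127 = 85 PET lesions, or 85/212 = 40.1%, was undetermined. A per-man score would show none of this. That series used prostatectomy histology, so it does not predict the result against biopsy.

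**The case against.** The strongest reply is that 3.2 never says the focus is the unit of analysis. Read with 2.1 and the specific aim in 1.1, which is to detect cancer within the gland, a per-man call could be taken as a coarse version of the endpoint. This does not survive the reference standard that 3.2 names: PET is to be "compared with tumor maps derived by histology of biopsy specimens obtained guided biopsy", and a yes/no call per man cannot be compared with a map. The Schema adds localization, which a per-man call cannot address. It is fair that accuracy fits 2.1, that the intent to compare foci is stated, and that the form captures them. What is missing is a matching rule and a statistic.

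On sensitivity and specificity, the reply is that the hypothesis in 1.1 is broader than this study, that section 7.1 disclaims an efficacy purpose, and that the separate intervals would be barely informative on 12 and 8 men. The imprecision is real. It is a reason for caution in interpretation, not for reporting only a figure that hides the split. The same 20 results supply both estimates.

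Two smaller points stand. Whether 60% falls inside the interval for 16/20 depends on the method, so the conclusion should not rest on step 4. The 212 against 127 comparison is illustration only.

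**Conclusion.** The concern holds on both counts. The primary endpoint in 3.2 has no planned estimate, and the ±17.5 points applies only to patients. The one planned summary cannot distinguish sensitivity 100% with specificity 50% from sensitivity 67% with specificity 100%. Those figures assume the plan's 60% cancer rate and exactly 16 of 20 correct; at other rates the split changes but the ambiguity remains. The mismatch is with 3.2 and the Schema, not with 2.1. The study remains usable, and the plan should be corrected before analysis.

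**What to change.** 1. In section 7, add patient-level sensitivity and specificity against biopsy histology, each with an exact 95% interval, alongside accuracy.
2. Reconcile 3.2 with 2.1 and section 7 in one of two ways:
   - restate the primary endpoint at patient level and make the foci comparison a descriptive secondary analysis (the simpler repair); or
   - keep the foci endpoint and add a sextant-level analysis limited to sampled sextants, with a matching rule, an interval that allows for clustering within patient, and PET foci in unsampled sextants reported as unverified.
3. In either case, state that 80% ±17.5 points refers to patients.

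As a supporting step, define the patient-level PET call in advance and date it before pathology is known. This is feasible because section 6.1 schedules PET "at least one week but not more than 3 weeks before their scheduled" biopsy.

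**Cost.** No extra patients or procedures; the change is to wording in 3.2 and section 7. If foci stay primary, confirm that the PET and biopsy forms record location for every sextant. The PET form as provided shows only the left-sided ones and may be cut off, so nothing is inferred about the full form.

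**Downside.** The separate intervals are wide. If sensitivity and specificity were each 80% (an assumption, since the documents give neither), the Wald half-widths would be 1.96 × √(0.16/12) = 22.6 points and 1.96 × √(0.16/8) = 27.7 points. At a cancer rate of one third (about 7 and 13 men) they would be 29.6 and 21.7 points. A sextant analysis limited to sampled tissue has a smaller denominator, is open to partial-verification bias, and rests on at most 20 clusters.
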